16.3 The query process

The Monitor will review the eCRFs and evaluate them for completeness and consistency. Data in the eCRF will be compared with the respective source documents to ensure that there are no discrepancies for critical data as described in the RBM plan.

If corrections are needed, queries will be raised within the eCRF, either as a result of built-in edit checks or manually raised by the Monitor. An appropriate member of the site staff will answer the queries in the eCRF either by correcting the data or by entering a response to the query. The Monitor will either approve the answer/correction or re-issue the query.

16.4 Audit trail

All entries in the eCRF will be fully recorded in a protected audit trail. Once clinical data have been saved, corrections to the data fields will be audit trailed, meaning that the reason for change, the name of the person who made the change, together with time and date will be logged.

16.5 External data

External data consists of data that are not recorded in the eCRF. Data may be received in electronic format. Key variables are defined in order to uniquely identify each sample record. File and data formats are agreed with the external data provider.

16.6 Medical coding

Medical coding will be performed by trained personnel at CTC. AEs and medical/surgical history verbatim terms will be coded using the Medical Dictionary of Regulatory Activities (MedDRA; latest version available at start of eCRF development). Prior and concomitant medications will be coded according to the WHO Anatomic Therapeutic Chemical (ATC) classification system. All coding will be approved by the Sponsor prior to database lock.

16.7 Database lock

When all data have been entered and discrepancies solved, clean file will be declared, the database will be locked, and the data will be analyzed.

CONFIDENTIAL 52 (59)

17 STATISTICAL METHODS AND DETERMINATION OF SAMPLE SIZE

The principal features of the statistical analysis to be performed are described in this section. A more technical and detailed elaboration of the principal features will be presented in a separate Statistical Analysis Plan (SAP), which will be signed and approved prior to database lock.

17.1 General

Continuous data will be presented with descriptive statistics in terms of evaluable and missing observations, arithmetic mean, standard deviation (SD), median, minimum and maximum value, Q1-Q3 (interquartile range [IQR]). In addition, for the parameters AUC and C_{max} the geometric mean and coefficient of variation (CV) will be presented.

Categorical data will be presented as counts and percentages. When applicable, summary data will be presented by IP, and by assessment time. Individual subject data will be listed by subject number, IP, and, where applicable, by assessment time.

All descriptive summaries and statistical analyses will be performed using SAS Version 9.4 or later (SAS Institute, Inc., Cary, NC).

Baseline will be defined as the last data collection time point prior to each IP administration.

No adjustment for multiple comparisons will be performed. All formal comparisons will be made towards a designated reference product and all significant findings will be reviewed for medical relevance.

No imputation of missing data will be performed.

17.2 Determination of sample size

Previous studies [6,7] have shown that the *in vivo* extracted fraction of nicotine has a CV ranging between 31-33%, and similar CVs for AUC_{inf}. Assuming no difference between products, defining equivalence as a 90% CI of least squares means (LSMeans) entirely in the range 0.8-1.25, and using a CV of 32.5%, a power of 80% and a significance level of 10 %, 36 evaluable subjects will be needed. To account for a dropout rate of 15%, 42 subjects will be randomized.

17.3 Pharmacokinetic analysis

The PK analysis will be based on the pharmacokinetic analysis set (PKAS) and performed by CTC. The PK parameters will be calculated by NCA using the software Phoenix WinNonlin® version 8.1 or later (Certara Inc, Princeton, New Jersey, U.S.A.). In addition to AUC_{inf} and terminal elimination half-life ($T_{1/2}$) parameters, other non-compartmental PK parameters will be determined in relation to secondary endpoints (see Section 17.7.2 below). Where possible, both baseline-adjusted and non-adjusted PK parameters will be calculated.

For AUC_{inf} , the area under the plasma concentration vs. time curve will be calculated to the time point of the last quantifiable plasma concentration of nicotine and then extrapolated to infinity using the concentration in the last quantifiable sample and the estimated terminal elimination rate constant (Lambda_z).

PK data will be presented for each IP using summary statistics. This data will be presented in terms of N, arithmetic mean, SD, minimum and maximum value. For AUC and C_{max}

CONFIDENTIAL 53 (59)

parameters, the geometric mean and CV will be presented. Categorical data will be presented as counts and percentages as applicable.

17.4 Analysis data sets

17.4.1 Full analysis set

The Full Analysis Set (FAS) will consist of all subjects who have been randomized and received at least 1 dose of IP and who have at least 1 post-baseline data point. This population will be used as the safety analysis set.

17.4.2 PK analysis set

The PK analysis set (PKAS) will consist of all subjects who received at least 1 IP administration and provided at least 1 evaluable PK-profile and no major deviation judged to compromise the PK analysis. Individual PK values and/or full profiles for explicit IPs may be excluded from the analysis as specified in the SAP.

17.4.3 Additional analysis datasets

Additional datasets may be created as needed for exploratory analyses.

17.5 Description of study population

17.5.1 Demographics and baseline characteristics

Demographics, weight, height, BMI as well as history of oral tobacco/nicotine use, and smoking will be presented by descriptive statistics. All data will be listed by subject.

17.5.2 Medical/surgical history and prior/concomitant medication

Medical/surgical history will be presented by system organ classes (SOC) and preferred term (PT). Prior/concomitant medications will be presented by ATC level 1, 3 and 5 through descriptive statistics and listings.

17.5.3 Treatment compliance

The number of subjects treated with each IP will be presented through descriptive statistics and listings.

17.5.4 Physical examination, ECG, and vital signs

Any abnormal findings at screening, *i.e.*, judged as outside the normal ranges by the Investigator, will be categorized as "abnormal, not clinically significant" or "abnormal, clinically significant" and presented in listings.

CONFIDENTIAL 54 (59)

17.6 Analysis of primary endpoint

17.6.1 Analysis of equivalence of ZYN Dry Smooth and ZYN Dry Virginia Blend (AUCinf)

The primary endpoint is the equivalence in AUC_{inf} after the administration of single doses of unflavored ZYN Dry Smooth 6 mg *vs.* the flavored ZYN Dry Virginia Blend 6 mg.

AUC_{inf} will be calculated as described in Section 17.3 above.

Equivalence will be assessed using a mixed model with the natural log of AUC_{inf} as the dependent variable, treatment as a fixed effect and subject as a random effect. The Kenward-Rogers approximation for degrees of freedom will be used. The estimated LSMeans difference between ZYN Dry Smooth and ZYN Dry Virginia Blend will be back-transformed into the original scale to present the ratio of geometric LSMeans as well as the corresponding 90 % confidence interval. If the 90 % confidence interval of this ratio falls within the range 0.8-1.25, the IPs will be considered equivalent. The model will be estimated for both non-adjusted and baseline-adjusted AUC_{inf} .

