8 STUDY DESIGN

8.1 Overall study design and schedule of events

This is an open-label, randomized, 9-way cross-over, single dose administration study designed to assess the impact of flavors in OTDN pouches on nicotine exposure. The IPs are OTDN pouches, ZYN Dry 6 mg: including 1 unflavored product (ZYN Dry Smooth) and 8 flavored products (ZYN Dry Virginia Blend, Kentucky Bold, Cherry, Dragonberry, Peach, Wine, Bourbon and Dark Rum).

The study will include 42 randomized subjects with the aim to achieve 36 fully evaluable subjects. The subjects are healthy male or female oral tobacco/nicotine pouch users aged \geq 21 years who have used oral tobacco/nicotine products for \geq 1 year, with a minimum daily consumption of 5 or more pouches. An effort will be made to randomize at least 17 female subjects (~40 %) in the study.

The subjects report to the clinic for a screening visit (Visit 1) followed by 9 treatment visits (Visit 2-10) on separate days. Screening (Visit 1) will take place within 4 weeks prior to Visit 2 and will include an eligibility check, including evaluations of smoking and oral tobacco/nicotine product use, a brief physical examination, laboratory tests, electrocardiograms (ECG) and collection of medical history, vital signs (pulse rate and blood pressure), height, weight, and body mass index (BMI, see Table 8.1-1 for details).

Subjects shall abstain from oral tobacco/nicotine products as well as smoking (cigarettes or e-cigarettes) for at least 12 h prior to each treatment visit (Visit 2-10). To this end, subjects will be instructed to avoid using such products from approximately 20:00 (8 pm) the day before treatment visits. All IP administrations are performed during the morning hours (08:00 to 12:00) to facilitate abstinence. Subjects should certify abstinence before each treatment starts.

The IPs will be administered as single pouches in a pre-determined randomized order. Subjects will keep the pouch still between the upper lip and gum for 60 min and will be instructed not to manipulate the pouch with the tongue or lips. They will also be instructed not to eat or drink, chew gum, or brush their teeth for 30 min before, during, or 30 min after the IP administration [12].

After 60 min each used pouch will be collected and frozen (-20°C) pending analysis of residual nicotine content. Unused pouches from the same batch will serve as references and will be stored at -20 °C pending analyses.

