Blood samples for the assessment of nicotine plasma levels and PK parameters will be collected at pre-defined time points from pre-administration to 6 h after each IP administration. The PD effects of the IPs will be determined using pulse rate measurements and subjective parameters (using VAS questions) at the same pre-defined time points as well as an MCQ 60 min after IP administration.

The total duration for each subject in the study will be approximately 5 weeks, not including the preceding 4-week screening period.

See Table 8.1-2 for a detailed schedule of events applicable for each treatment visit.

Study assessments are described in Section 11.

CONFIDENTIAL 24 (59)

Table 8.1-1 Schedule of events

Events	Visit 1 Screening	Visit 2 First treatment visit	Visit 3-10 Treatment visits		
Informed consent	X				
Demographics	X				
Medical/surgical history	X				
History of nicotine use	X				
Inclusion/exclusion criteria	X	X ¹			
Physical examination	X				
Weight and height, BMI	X				
Vital signs (blood pressure and pulse)	X				
Electrocardiogram	X				
HIV, Hepatitis B and C	X				
Pregnancy test ²	X	X ³	X^3		
Urine drug screen ⁴	X	X			
Alcohol screen ⁴	X	X			
Randomization		X			
IP (pouch) administration		X ⁵	X ⁵		
PK blood sampling (plasma)		X ⁵	X ⁵		
Subjective effects (VAS questions and MCQ)		X ⁵	X ⁵		
Pulse rate (pulse oximeter)		X ⁵	X ⁵		
IP (pouch) collection		X ⁵	X ⁵		
Baseline symptoms	X	X			
Adverse events		X	X		
Prior and concomitant medications	X	X	X		

CONFIDENTIAL 25 (59)

¹Confirmation of eligibility criteria.

² Only subjects of child-bearing potential.

³ Only at the discretion of Investigator. Only at the discretion of PI on Visits 2-10.

⁴ Additional drug and alcohol tests may be performed at the discretion of the Investigator during treatment visits.

⁵ The detailed timing of assessments is outlined in Table 8.1-2.

Table 8.1-2 Detailed schedule of events for each treatment visit (Visit 2-10)

	Visit 2 - 10															
ssessment / Time-point	Admission	-00:15	-00:10	-00:01	00:00	50:00	00:10	00:15	00:30	00:45	01:00	01:15	01:30	05:00	04:00	00:90
Inclusion/exclusion criteria	X ¹															
Urine drug screen	X ²															
Alcohol screen	\mathbf{X}^2															
Pregnancy test	X^3															
Randomization	X ⁴															
IP (pouch) administration					X ⁵											
IP (pouch) collection											X ⁵					
PK blood sampling (plasma)			X ^{5, 6}			X ⁵										

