9.9 Randomization

On Visit 2, the subjects will be randomized to 1 of 6 IP administration sequences. As this is an open-label study, the IP administration sequence to which each subject is allocated for will be recorded in the eCRF. A computer-generated randomization list will be created using SAS

CONFIDENTIAL 31 (59)

Proc Plan, SAS Version 9.4 or later (SAS Institute, Inc., Cary, NC). The randomization list will contain subject number, IP administration sequence, period, and IP.

The randomization list will be generated by CTC and a copy of the randomization list will be provided to the packing company and to the clinic. The original randomization list will be kept by the randomizer.

Because this is an open-label study, no blinding procedures will be followed.

CONFIDENTIAL 32 (59)

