17.7 Analysis of secondary endpoints

17.7.1 In vivo extracted amount and fraction of nicotine

The difference between the nicotine content of an unused reference pouch and the used study pouch will be used to calculate the *in vivo* extracted amount of nicotine for each IP. The mean of the extracted amount (mg/unit) and extraction fraction (%) of nicotine for each IP pouch will be calculated. The amount of nicotine in the reference pouches and in used pouches will be presented through descriptive statistics.

17.7.2 Pharmacokinetics of nicotine in plasma: Unflavored ZYN Dry Smooth vs. flavored ZYN Dry products

The following non-compartmental PK parameters will be determined for each IP: AUC_{inf} , AUC_{0-last} , $AUC_{0-l.5h}$, C_{max} , T_{max} and $T_{1/2}$. Where possible, both baseline-adjusted and non-adjusted PK parameters will be calculated.

 C_{max} and T_{max} will be derived from the observed nicotine plasma concentration data. AUC_{0-1.5h} and AUC_{0-last} will be calculated using log-linear trapezoidal interpolation. Calculations will be based on the actual sampling times recorded during the study. Concentrations below the lower limit of quantification (LLOQ) occurring before C_{max} will be treated as zero. Concentrations below LLOQ occurring after C_{max} will be omitted from the analysis. All baseline-adjusted PK parameters will be corrected for nicotine plasma concentrations at baseline (pre-administration).

AUC_{inf} will be calculated as described in Section 17.3 above.

The equivalence in AUC_{inf} and C_{max} between the unflavored ZYN Dry Smooth (comparator product) and each flavored ZYN Dry product will be estimated as for the primary endpoint, described in Section 17.6.1. Equivalence will be estimated for both non-adjusted and baseline-adjusted AUC_{inf} and C_{max} .

CONFIDENTIAL 55 (59)

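### The equivalence model omits period in a 9-period cross-over; a period term should be added, although the size of the harm is unknown and probably modest

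*Protocol*

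**What the plan says.** Protocol section 8.1 describes an "open-label, randomized, 9-way cross-over, single dose administration study", with nine treatment visits per subject: "The total duration for each subject in the study will be approximately 5 weeks", screening not counted. Section 9.9 states that "the subjects will be randomized to 1 of 6 IP administration sequences" and that "The randomization list will contain subject number, IP administration sequence, period, and IP".

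Section 17.6.1 then fixes the primary analysis: a mixed model for the natural log of AUCinf with "treatment as a fixed effect and subject as a random effect", Kenward-Roger degrees of freedom, and the back-transformed ratio with its 90% interval. The decision rule is: "If the 90 % confidence interval of this ratio falls within the range 0.8-1.25, the IPs will be considered equivalent". Section 17.7.2 says that equivalence in AUCinf and Cmax for each flavored product "will be estimated as for the primary endpoint". Neither section includes period. Section 8.2 deals with carryover through abstinence from nicotine, but the protocol does not discuss period effects.

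**The concern.** In a cross-over, whatever changes from visit to visit for everyone (familiarity with the procedure, sampling or assay conditions, habits over the weeks of participation) is a period effect. A treatment-plus-subject model has nowhere to put it, so one of two things happens.

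- If the two products in a contrast do not occupy the same visits equally often, part of the period effect enters their estimated ratio.
- If they do, the ratio is unaffected, but the variation between visits stays in the residual and the interval becomes wider than it need be.

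The conclusion rests on one 90% interval against 0.8-1.25, and planned power is barely 80%, so there is little slack for either. The same model decides equivalence for the other seven flavors.

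**Working it through.** **Inputs from the protocol.** CV 32.5%, 36 evaluable subjects, 80% power, 90% interval within 0.8-1.25, true ratio 1 ("Assuming no difference between products"), 15% dropout (section 17.2); nine products in nine periods (8.1); six sequences (9.9). The size of any drift is not in the protocol. It is an assumption below and is shown as a range.

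**1. The plan's own figure.** Log-scale within-subject SD = sqrt(ln(1 + 0.325²)) = 0.3169. Standard error of a product contrast = 0.3169 × sqrt(2/36) = 0.0747. Two one-sided tests at 5% with n − 2 = 34 df give exact power of 80.03% at n = 36, and less than 80% at n = 35. The 36 is reproduced.

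For the nine-period model, residual df = 36 × 9 − 1 − 35 (subjects) − 8 (products) = 280, and power is 81.8%. With period, df = 280 − 8 = 272, and power is still 81.8% if products are balanced over visits.

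**2. Can design balance be relied on?** With six sequences and equal numbers on each, a product occupies six sequence-by-visit cells spread over nine visits. Since 6/9 is not a whole number, no product can appear equally often at every visit. In 20,000 simulated lists made of six rows of a 9×9 Latin square, the gap in mean visit position between two given products had median 0.67 visits, 95th percentile 1.83 and maximum 3.0; about 10% of lists reached 1.6. With six unrestricted random orders about 32% reached 1.6. A full nine-row Latin square with equal numbers per row has a gap of zero.

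**3. Shift of the ratio when products are unbalanced.** Shift = (1 + drift per visit)^gap. Power is taken at a true ratio of 1. The error is the probability of declaring equivalence at a true ratio of 1.25 when the shift points toward 1, so the effective ratio is 1.25/shift (n = 36, df 280).

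| Assumed drift per visit (first to ninth visit) | Gap | Shift | Power | Error at margin |
|---|---|---|---|---|
| none | any | 1.000 | 81.8% | 5.0% |
| 1% (1.01^8 = 1.083) | 0.67 | 1.007 | 81.7% | 6.0% |
| 1% | 1.83 | 1.018 | 80.5% | 8.1% |
| 2% (1.02^8 = 1.172) | 0.67 | 1.013 | about 81.1% | 7.1% |
| 2% | 1.83 | 1.037 | 76.8% | 12.3% |
| 3% (1.03^8 = 1.267) | 0.67 | 1.020 | 80.3% | about 8% |
| 3% | 1.83 | 1.056 | 71.0% | 17.8% |

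If the shift points away from 1, the error at the margin falls below 5% instead. The direction depends on the list.

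**4. Width of the interval when products are balanced.** Inflation of the log-scale half-width = sqrt(1 + τ²/0.1004), where τ is an assumed SD of the period effects and 0.1004 = 0.3169². For τ = 0.05, 0.10 and 0.15 the interval widens by 1.2%, 4.9% and 10.6%. At an observed ratio of 1 the upper limit moves from 1.131 to 1.133, 1.138 and 1.146.

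**5. Price of the period term.** With balance it is the 8 df of step 1. With six sequences products and periods are not orthogonal. The information on products after removing subjects and periods is proportional to 6I − NN′/6, where N counts each product at each visit over the six sequences. For six rows of a Latin square, the variance of a given pairwise contrast rises by a median factor of 1.06 (sqrt = 1.03 on the standard error), which leaves power at about 79%.

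**The case against.** The harm depends on a drift that the protocol neither states nor suggests, and several provisions limit it. Subjects are established daily users who do not intend to change their habit; every session follows at least 12 h of abstinence, in the morning, with one pouch held still for a fixed 60 min; and the primary parameter is baseline-adjusted. At about 1% per visit and a typical gap, power barely moves. This stands, and it is why the size is given as a range.

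A reader might infer that the Virginia Blend ratio will be biased by several per cent. The documents do not support that. Order is randomized, so over randomly generated lists the expected shift is zero; the shift belongs to the list drawn. A chosen set of six sequences could also equalize mean visit position for the one primary pair against a linear drift, though it could not give every product equal representation at each visit. Shifts of 3-6% need a gap in the tail of the distribution as well as the assumed drift. Withdrawn subjects may also be replaced (section 9.8.3), which limits imbalance from dropout.

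A reader might also infer that leaving out sequence is a fault of the same kind. Sequence is a between-subject term that hardly touches a within-subject contrast, and no effect of omitting it has been shown.

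Finally, section 17 leaves technical detail to a SAP that is to be signed before database lock. That SAP could add the term. But section 17.6.1 already names the response, fixed effect, random effect, df method and decision rule, so a SAP that follows it inherits the omission.

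**Conclusion.** The point holds as a should-fix. The model is stated in full without a period term, in a design with nine periods and, as written, an allocation that cannot balance products over visits when sequence numbers are equal. The effect is a shift of the ratio for the list drawn, or a wider interval, or some of each.

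With 2% drift per visit assumed, the typical consequence is a shift of about 1.3% and an error at the margin of about 7% if it points toward 1. The tail case is about 3.7%, with power about 77%. With balance, assumed period SDs of 5-15% widen the interval by about 1-11%. With no drift nothing is lost. The documents do not show that the planned analysis would reach a wrong conclusion, and the omission does not by itself invalidate the trial. The case for the change is that it protects the error rate at low cost and is best settled before data are seen.

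**What to change.** In section 17.6.1, and hence section 17.7.2, add period as a nine-level fixed effect to the ln(AUCinf) and ln(Cmax) models. Keep treatment fixed, subject random and Kenward-Roger degrees of freedom. A sequence term is optional, by convention only. State the same model in the SAP before database lock.

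The cost is one sentence. No data collection changes, because period is already on the randomization list. In a design balanced over visits the term uses 8 of 280 residual df and leaves power at 81.8%. If six sequences are kept, it also adds about 3% to the standard error in the Latin-square case, which is the price of removing the shift.

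The mismatch between six sequences and nine products in section 9.9 should be reconciled as a separate point. Balancing products over visits would remove that extra cost.
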